# 5.7 Statistical analysis

The individual patient was used as statistical unit. All analyses were performed on patient level. BOP was defined as the main outcome variable and GBI as secondary outcome variable. All other parameters were control variables.

For all individuals, cigarette pack years were calculated. Group frequencies (VWD, control) were expressed for sex, current smoking. Group means and standard deviations were calculated for GBI, BOP, age, number of remaining teeth, pack years, CO, PCR, Body weight, VWF:Ag, VWF:RCO, FVIII:C, Hb1c. Further, for each individual the following variables were calculated to describe the periodontal status:

- Mean±standard deviation of PPD and PAL-V
- Percentage of PPD < 4 mm, 4 to 6.8 mm, ≥ 7 mm
- Sum of all PPD (Wohlfeil et al. 2009), i.e. the sum the PPD measured at all sites within a patient
- Sum of all PPD with BOP (Wohlfeil et al. 2009), i.e. the sum the PPD measured at all sites exhibiting BOP within a patient
- Periodontal inflamed surface area (PISA) [20, 21]. For each patient PPD were entered into an Excel sheet that can be downloaded freely (http://www.parsprototo.info/pisa.html).

From these group means and standard deviations were calculated. Comparisons between groups for dichotomous parameters were made by  $\chi^2$  or Fisher's exact test and for all other parameters by Mann-Whitney-U test. A post-hoc analysis was performed to estimate the test power that would be required to find a clinically relevant inter-group difference ( $\delta$ ) of 5.5% for BOP and GBI index with a type 1 error ( $\alpha$ ) of 0.05 for the actual sample size.

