Using stepwise linear backward multiple regression analysis, factors should be identified that influenced BOP and GBI. The following independent variables were entered into the model for BOP: group (VWD/control), VWD type 2 or 3, sex, age, body weight, HbA1c, PCR, CO, aMMP-8, number of remaining teeth, PISA. The following independent variables were entered into the model for GBI: group (VWD/control), VWD type 2 or 3, sex, age, body weight, HbA1c, PCR, CO, aMMP-8, number of remaining teeth, PISA. Due to the fact that mean PPD is mathematically coupled to sum of PPD, sum of PPD with BOP, and PISA these 4 variables were not entered into the regression model at the same time. PISA provides the best representation of the subgingival inflamed area. Thus, PISA was chosen for the final model. The following parameters were described by dummy variables: group (control = 0, VWD = 1), sex (male = 0, female = 1), smoking status (never and former smoker = 0, current smoker = 1). All factors with p < 0.05 were kept in the models. For statistical analysis a PC program was used (SystatTM for Windows Version 13, Systat Inc., Evanston, USA).

[name] & [name] (143/15: Version 2: 27.05.2015)

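### Group (VWD/control), the study's exposure, stays in the BOP and GBI regressions only if p < 0.05, so an adjusted VWD–control difference with a confidence interval may not be reported

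*Combined protocol and SAP*

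**What the plan says.** Section 5.7 (Statistical analysis) describes a backward stepwise linear regression meant to identify factors that influence BOP and GBI. Both models start from the same 11 candidates: "group (VWD/control), VWD type 2 or 3, sex, age, body weight, HbA1c, PCR, CO, aMMP-8, number of remaining teeth, PISA". The retention rule is "All factors with p < 0.05 were kept in the models". No sentence forces group in, exempts it from the rule, or says that full-model coefficients will be shown.

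Coding is given for group, sex and smoking status ("The following parameters were described by dummy variables: group (control = 0, VWD = 1), sex (male = 0, female = 1" and so on), but not for VWD type.

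The direct comparison in the same section is unadjusted: "Group means and standard deviations were calculated for GBI, BOP, age, number of remaining teeth" and further variables, then a Mann-Whitney U test for non-dichotomous parameters. A post-hoc power estimate for 5.5% follows. No confidence interval is named, crude or adjusted.

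Section 3.1 hypothesises that gingival bleeding in type 2 and 3 VWD comes mainly from periodontal inflammation rather than from VWD. Section 5.3 plans 31 per group for a 5.5% difference and reports analysis with 24 per group.

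**The concern.** The aim in section 3.2 is to separate VWD from periodontal inflammation as the cause of bleeding. The quantity that speaks to this is the VWD–control difference after adjustment for plaque and the other factors the sponsor selected. Treating the exposure as just another candidate makes the reporting of that quantity depend on its own p-value.

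This matters more than usual because the hypothesis is close to a claim of little or no VWD effect. Deletion of group could be read as agreement with it, and the documents do not say how deletion is to be interpreted. Section 5.7 calls 5.5 points clinically relevant. Without an estimate and interval, nobody can see whether 5.5 points remains possible after adjustment, and a post-hoc power figure does not answer that.

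The type term adds a further difficulty. It is nested within group (controls have no type), so what the group coefficient means depends on a coding that is not stated.

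**Working it through.** **Inputs.** From sections 5.3 and 5.7: difference 5.5 points, alpha 0.05, power 80%, 31 per group planned, 24 per group analysed. Assumed: two-sided test (sidedness is not stated), normal outcome, covariates unrelated to group. No SD is given.

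**1. SD implied by the planned size.** From n = 2(z₀.₉₇₅ + z₀.₈₀)² SD²/δ²:

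SD = 5.5 / [(1.960 + 0.842) × √(2/31)] = 5.5 / (2.802 × 0.2540) = 7.7.

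The t-based version gives 7.6, used below. A one-sided test would give about 8.7. The range 6 to 10 covers both. The planned 62 can only be back-solved in this way, not checked independently.

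**2. Chance that group is dropped when the true excess is 5.5.** At 24 per group the SE is 7.6 × √(2/24) = 2.19 and the noncentrality is 5.5/2.19 = 2.51. Power on 46 df is 0.689, so 1 − 0.689 = 31%. A simulation of backward elimination at 0.05, with all other covariates (including PISA) unrelated to the outcome and no type term, dropped group in about 32% of runs (15% at SD 6, 54% at SD 10). In a similar simulation the planned Mann-Whitney test was non-significant in 33% to 34%. Elimination therefore adds no missed detections here.

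**3. What is reported when group survives.** In simulation at SD 7.6, the mean retained estimate was about 6.7 for a true 5.5. Estimates shown only when significant are too large on average.

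**4. Interval available if group is forced in.**
- Crude: t₀.₉₇₅,₄₆ × SE = 2.013 × 2.19 = 4.4.
- Adjusted, group plus nine covariates all kept: residual df = 48 − 11 = 37 and t = 2.026. Nine unrelated covariates explain on average 9/47 = 0.19 of the variance of group, which inflates the SE by 1/√(1 − 0.19) = 1.11. Half-width = 2.026 × 2.19 × 1.11 = 4.9.
- The same calculation gives 3.9 at SD 6 and 6.5 at SD 10. Simulated coverage was 94% to 96%.
- If the covariates are instead stepwise-selected around a forced group term, the half-width is about 4.3, narrower than the crude 4.4 although the covariates are noise. That is a selection artefact, so 4.9 is the figure to quote.

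**5. What deletion can hide.** With half-width 4.9, a group estimate is non-significant whenever it lies within ±4.9. The interval excludes 5.5 only if the estimate is below 5.5 − 4.9 = 0.6. An estimate between 0.6 and 4.9 would thus be non-significant and still compatible with the study's own relevant difference.

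**The case against.** The regression's stated purpose is to identify factors, not to estimate the VWD effect. The group comparison is the Mann-Whitney test, made after matching on sex, age, smoking, number of teeth and diagnosis (section 5.2). The planned means and SDs let a reader derive a crude interval. Backward elimination starts from a full model that contains group, and nothing forbids reporting it. All of this stands, and it is why the point is that the adjusted difference may not be reported. A reader might infer that it certainly will not be; the text does not go that far. What remains is that neither the matching nor the crude interval adjusts for plaque, HbA1c, CO, body weight or aMMP-8, which the sponsor itself chose as candidates.

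A second tempting reading is that elimination makes the study miss real VWD effects. Steps 1 and 2 do not support it: the 31% is 1 minus power. With the type term coded 0/2/3 and five type 3 cases (both assumptions), group was dropped in 56% of simulated runs. Both terms were lost in only 30%, so the 56% is not a loss of the VWD signal either.

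A third is that PISA, as a covariate for BOP, is partly built from bleeding and absorbs the group effect. Section 5.7 says "PISA provides the best representation of the subgingival inflamed area" and that "mean PPD is mathematically coupled to sum of PPD, sum of PPD with BOP, and PISA"; one of these is defined as "the sum the PPD measured at all sites exhibiting BOP within a patient". But the coupling described may be through depth alone, and the only stated input is depth: "For each patient PPD were entered into an Excel sheet". The formula is not given. If PISA were BOP times lognormal noise, a forced-in group estimate for a true 5.5 would average 2.6, 4.5 or 5.2 at log-SD 0.3, 0.6 or 1.0. These figures follow from the assumed link and do not show that the link exists.

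**Conclusion.** The point holds in a limited form. As written, reporting of the adjusted VWD–control difference for BOP and GBI depends on its significance, no interval is planned, and the uncoded type term blurs the meaning of the group coefficient. The loss is an estimate and interval to set against 5.5 points. With a true 5.5-point excess, group would be dropped in about 31% of studies at SD 7.6; this rests on the back-solved two-sided SD and reflects 69% power.

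A reader might also infer that the sponsor intends deletion of group to count as proof of the hypothesis. The documents do not say so; the concern is that nothing rules the reading out. Whether PISA distorts the BOP model cannot be decided from the documents, so that part of the remedy is conditional. This should be corrected, but it does not invalidate the planned unadjusted comparison.

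**What to change.** - For BOP and for GBI, fit one model with group forced in and a fixed covariate set drawn from section 5.7: sex, age, body weight, HbA1c, PCR, CO, aMMP-8, number of teeth and one measure of periodontal severity. Leave out the VWD type term.
- Report the group difference with its 95% CI whatever the p-value, and compare the interval with 5.5 points.
- Describe types 2 and 3 separately within the 24 cases.
- Label the stepwise models exploratory. State that non-retention or non-significance of group is not evidence for the hypothesis.
- State how PISA is computed. If it uses bleeding sites, take mean PPD (already planned) as the severity measure in the main BOP model and show PISA as a sensitivity analysis. Otherwise show the estimate with each. Adjusting for mean PPD assumes that VWD does not itself change pocket depth.

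Cost: a few model runs on existing data, labelled post hoc because section 5.3 reports the study as already analysed. No new patients or measurements are needed. The interval will be wide, at about ±4.9 points for SD 7.6 (±3.9 to ±6.5 over SD 6 to 10) if the covariates explain little of the outcome, and forcing group in adds no power.

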# 5.3 Fallzahlschätzung

A sample size of n = 62 (31 VWD cases and 31 controls) was required to detect an inter-group difference of 5.5% [4] GBI or BOP with a type 1 error  $\alpha$  < 0.05 and a test power of 80% (http://jumbo.uni-muenster.de/fileadmin/jumbo/applets/falla.html). After inclusion of 24 type 2 and 3 VWD cases no further type 2 and 3 VWD cases could be recruited at the Haemophilia Centre, Medical Clinic III/Institute for Transfusion medicine, Hospital of the Johann Wolfgang Goethe-University Frankfurt/Main. Thus, the study was analyses with 24 cases and 24 matched controls.

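### Backward elimination of 11 candidates at p < 0.05 in 48 participants makes the retained factors exploratory, not confirmatory, evidence on VWD versus inflammation

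*Combined protocol and SAP*

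**What the plan says.** The regression in section 5.7 is introduced with its purpose: "Using stepwise linear backward multiple regression analysis, factors should be identified that influenced BOP and GBI". The candidate list opens "The following independent variables were entered into the model for BOP: group (VWD/control), VWD type 2 or 3, sex, age, body weight, HbA1c, PCR" and ends "PCR, CO, aMMP-8, number of remaining teeth, PISA". The same variables are listed for GBI. The retention rule is "All factors with p < 0.05 were kept in the models". Section 5.3 gives the sample: "Thus, the study was analyses with 24 cases and 24 matched controls".

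The plan adjusts for no multiplicity in this search, does not force group to stay, describes no validation or shrinkage, and does not call the analysis exploratory. It gives a dummy code for group but none for VWD type.

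Separately, section 5.7 compares BOP and GBI between groups by the Mann-Whitney U test. That comparison does not pass through the selection.

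**The concern.** Section 3.2 asks whether gingival bleeding in type 2 and 3 VWD comes from impaired coagulation or from periodontal inflammation. The Mann-Whitney test looks at group alone. The stepwise regression is the only described analysis that sets group against PCR, aMMP-8 and PISA together, so a reader will look there for the attribution.

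Backward elimination tests many candidates, keeps those that pass 0.05, and then reports p-values as if no search had taken place. With few participants per candidate, three things follow:

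- Some retained factors are noise.
- Weak real factors look too strong when they survive.
- Related inflammation measures compete, so which of them survives is partly chance.

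Calling the survivors factors that *influenced* bleeding gives them more weight than this procedure can carry.

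**Working it through.** **1. The plan's own figures.** The documents state no error rate for the regression, so there is none to reproduce. The only design figures concern the group comparison: "A sample size of n = 62 (31 VWD cases and 31 controls) was required", for an "inter-group difference of 5.5% [4] GBI or BOP", with alpha 0.05 and 80% power. The SD is not given. Solving 31 = 2 × (1.960 + 0.842)² × SD² / 5.5² (two-sided, assumed) gives SD ≈ 7.73 points. At 24 per group, power is Φ(5.5 / (7.73 × √(2/24)) − 1.960) = Φ(0.505) ≈ 69%.

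**2. Inputs for the search.** Candidates: group, VWD type, sex, age, body weight, HbA1c, PCR (7), plus CO, aMMP-8, number of teeth, PISA (4), total 11. Participants: 24 + 24 = 48, so 48/11 ≈ 4.4 per candidate. Threshold: 0.05 per factor.

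**3. Closed-form benchmark.** For 11 independent tests, 1 − 0.95¹¹ = 43.1%. For 22 tests over two outcomes, 1 − 0.95²² = 67.6%.

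**4. Simulated elimination.** Each run fits least squares with an intercept, drops the candidate with the largest p, and repeats until all p < 0.05. The outcome is normal noise. Runs per scenario: 4,000 to 20,000; Monte Carlo standard error at 8,000 runs is at most √(0.25/8000) = 0.6 points. All predictor correlations are assumptions.

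| Scenario, n = 48 | At least one factor kept | False factors per model |
|---|---|---|
| 11 independent candidates | 45% to 46% | about 0.68 |
| Matched-design-like predictors | 45% to 46% | about 0.71 |
| Pairwise correlation 0.3 | 46% to 47% | 0.72 to 0.77 |
| Pairwise correlation 0.6 | 50% | 0.92 |
| 10 candidates (type treated as duplicating group) | 43% | 0.62 |

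For BOP or GBI, at least one false factor appears in 70% of runs if the outcomes are independent, about 67% at outcome correlation 0.6, and 65% at 0.7.

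**5. PISA truly predictive.** With PISA as the only real predictor (standardised effect 0.5 or 0.8, assumed), at least one noise factor is still kept in 41% to 45% of models.

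**6. Factors that bear on the aim.** Under the null, at least one of PCR, aMMP-8 and PISA is kept in about 17% to 20% of models. Any single factor, including group, is kept about 6% of the time. Some retained factor reaches p < 0.001 in only 2% to 3% of null models.

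**7. Weak real factors.** With an assumed standardised slope of 0.2, the factor is kept in about 27% to 29% of runs and is then overstated about 1.85-fold. With 0.3, it is kept in 55% to 56% and overstated 1.33-fold.

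**8. A real group effect.** With a true difference of 5.5 points and SD 7.73 (implied in step 1), group is dropped from about 33% of models. When kept, its mean estimate is 6.7. Step 1 shows that a plain comparison would already miss the effect in 100 − 69 = 31% of studies, so the loss is mainly one of sample size. The overstatement comes from reporting only the estimates that pass 0.05.

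**9. R-squared.** With no signal, the full 11-variable model has expected R-squared 11/47 = 0.23. After elimination the average is about 0.07, or about 0.16 when anything is kept.

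**10. What deleting elimination would do.** In the unadjusted full model, some p < 0.05 still occurs in about 38% of null datasets. Holm adjustment over all 11 p-values brings this to about 4% to 5%. Most of the error is therefore multiplicity rather than the stepwise search itself.

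**The case against.** The strongest reply is that the selection is peripheral. The sample size is set on the group difference, the group comparison is a Mann-Whitney test, and the regression only looks for factors. This stands as far as it goes: the group comparison is untouched. It does not clear the regression, because no other described analysis weighs VWD against inflammation.

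A second reply is that a world in which PISA and PCR have no relation to bleeding is one that the protocol's own background rejects. That is fair, and the 46% is a benchmark rather than an expected rate of false findings. But noise factors enter at nearly the same rate when PISA is predictive (step 5).

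Three stronger readings are tempting, and the documents do not support them:

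- A reader might infer that inflammation would be falsely credited 46% of the time. Much of the 46% comes from sex, age, weight, HbA1c, CO or number of teeth, which do not decide between the two explanations. The relevant figure is 17% to 20%.
- A reader might infer that a surviving PISA term is probably noise, or that the study cannot address its aim. Neither follows: a very small p-value would still carry weight.
- A reader might take the 0.23 as the inflation of R-squared in the selected model. It belongs to the full model; the selected model averages about 0.07.

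**Conclusion.** The point holds as a matter of evidential status. With 11 candidates, an unadjusted 0.05 and 48 participants, about 46% of BOP models keep at least one factor when none is real (43% to 50% over the settings tried), and the selected factors and their p-values are exploratory evidence on VWD versus inflammation. Absence of group from a final model is likewise no evidence that VWD plays no part (step 8).

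The figures assume two-sided t-tests and normal errors, together with the stated correlations and slopes, none of which the documents give. They also depend on how VWD type is coded. The change is advisable and cheap. The point does not undermine the main group comparison.

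**What to change.** Drop elimination as the basis for inference. For BOP and for GBI, report one pre-specified model that always keeps group. Code VWD type so that it is not collinear with group, for example one type 3 indicator among cases. If type were entered as separate type 2 and type 3 indicators, group would be their exact sum and could not be estimated. With the single indicator, the group coefficient compares type 2 cases with controls, and the table should say so.

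Give every coefficient with its 95% interval, adjusted R-squared and the overall F test. Apply Holm adjustment to the nine non-exposure factors (11 less group and type), since removing elimination alone leaves the 38% of step 10. Label the factor search exploratory, and replace *influenced* by *were associated with*.

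The cost is some wording in section 5.7 and one table per outcome from existing data. The downside is wider intervals and fewer significant factors. About 4.4 participants per candidate, and the overlap among PCR, aMMP-8 and PISA, remain unless the list is shortened in advance; the intervals will at least show it.

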## 6. Time line

Laufzeit:June 2015 to December 2016Clinical and laboratory examination:June 2015 to December 2015Analysis and publication:January 2016 to December 2016

